### 9.5.5 Multiplicity

No adjustments for multiple testing will be utilized for any analyses.

### 9.5.6 Pooling of Sites

No pooling of sites will be used in any analyses.

## 9.6 Safety Analyses

Safety data will be summarized for the safety set separately for Phase 1 and Phase 2 Portions by treatment arm or dose level. For the Phase 2 Portion of the trial summaries will be by actual treatment received. Actual treatment for the Phase 2 Portion of the trial is defined as follows:

- Any subject who receives at least one dose of vadastuximab talirine will be assigned an “actual” treatment of vadastuximab talirine.
- Subjects who only receive azacitidine for the duration of the trial will be assigned an “actual” treatment of azacitidine.

### 9.6.1 Adverse Events

#### 9.6.1.1 Dose Limiting Toxicities

The incidence of DLTs will be summarized using the DLT evaluable set. The number and percentage of subjects experiencing a DLT and not experiencing a DLT will be presented for each dose level for the DLT evaluable set. The DLTs observed will be summarized by dose level and by MedDRA PT. DLTs will also be summarized by category of NCI CTCAE (version 4.03) grade by SOC and PT.

#### 9.6.1.2 Adverse Events and Serious Adverse Events

AEs will be summarized by descending frequency of MedDRA PT unless otherwise specified. For incidence reporting, if a subject reports more than one AE that was coded to the same SOC or PT, the subject will be counted only once for that specific SOC or PT. See [Section 5](#) for definition of pre-existing AEs, TEAEs, related AEs, SAEs, infusion-related reaction AEs and AEs leading to vadastuximab talirine treatment discontinuation. All the AEs summarized in tables are TEAEs, except related AEs or unless otherwise indicated. All AEs will be coded by SOC, MedDRA PT, and severity grade using NCI CTCAE. All recorded AEs will be included in the data listings.

A summary table of number and percent of the following AE categories will be provided by treatment or dose level and total as follows:

- Pre-existing AEs
- All TEAEs
- TEAEs related to vadastuximab talirine or placebo
- TEAEs related to azacitidine treatment
- TEAEs with outcome of death
- Treatment-emergent SAEs
- Treatment-emergent SAEs related to vadastuximab talirine or placebo
- Treatment-emergent SAEs related to azacitidine treatment

- TEAEs leading to dose delay of vadastuximab talirine or placebo treatment
- TEAEs leading to dose delay of azacitidine treatment
- TEAEs leading to dose interruption (full dose received) of vadastuximab talirine or placebo treatment
- TEAEs leading to dose interruption (full dose received) of azacitidine treatment
- TEAEs leading to dose being stopped early (full dose not received) of vadastuximab talirine or placebo treatment
- TEAEs leading to dose being stopped early (full dose not received) of azacitidine treatment
- TEAEs leading to dose reduction of vadastuximab talirine or placebo treatment
- TEAEs leading to dose reduction of azacitidine treatment
- TEAEs leading to treatment discontinuation
- Treatment-emergent SAEs leading to treatment discontinuation
- Vadastuximab Talirine -related TEAEs leading to treatment discontinuation
- Azacitidine -related TEAEs leading to treatment discontinuation
- Grade 3-5 TEAEs
- Grade 3-5 vadastuximab talirine or placebo treatment-related TEAEs
- Grade 3-5 azacitidine treatment-related TEAEs
- Infusion-related reaction TEAEs

All the above categories of AEs as well as TEAEs that started during infusion and TEAEs that started within 24 hours post infusion will be displayed by descending frequency of PT by total. TEAEs will be summarized by SOC, PT by treatment or dose level, and total. TEAEs will also be summarized by SOC, PT, maximum severity, treatment or dose level, and total. The listings include subjects with TEAE leading to treatment discontinuation. All AEs (including non-treatment-emergent events) recorded on the CRF will be listed.

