9.1.2 Phase 2 Portion – Randomized, Placebo-Controlled

Subjects will be randomized in a 1:1 manner to one of the study arms described in Table 1. Randomization will be stratified by Eastern Cooperative Oncology Group (ECOG) performance status (0 vs 1 or 2) and IPSS score (Intermediate-2 vs High risk).

[figure not shown]
Table 1: Treatment Arms

Study Treatment		Treatment Arm	
		Experimental	Comparator
Open-Label Study Treatment	Azacitidine 75 mg/m ² SC or IV (at the Investigator's discretion) for 7 days	X	X
Blinded Study Treatment	Vadastuximab talirine (SGN-CD33A) every 4 weeks (after azacitidine on the last day of azacitidine administration) via IV push at SMC-recommended dose	X	
	Placebo every 4 weeks (after azacitidine on the last day of azacitidine administration) via IV push		X

IV = intravenous; SC = subcutaneous; SMC = Safety Monitoring Committee.

Subjects will receive vadastuximab talirine in combination with azacitidine in 28-day cycles, starting at the dose level of vadastuximab talirine determined in phase 1. Response assessments (bone marrow examination and CBC) will be conducted once between Day 22 and Day 29 of even-numbered cycles until CR, then every 4 cycles thereafter. Subjects may continue on study treatment until disease progression, relapse, or unacceptable toxicity. After discontinuation of study treatment, subjects who have not had progression or relapse will continue to be assessed for response every 4 months through 24 months after EOT or until initiation of another anticancer treatment, progression, or relapse, whichever comes first. All subjects will be contacted for survival status every 2 months after EOT in follow-up until death or study closure, whichever comes first. Safety will be monitored through the surveillance of AEs, laboratory test measures, physical examination findings, and concomitant medication records. An IDMC (Section 13.6.10) will also periodically assess the ongoing safety data and make recommendations to either continue evaluating the combination or to stop the study due to toxicity concerns. Figure 2 is a study schematic for the Phase 2 Portion.

Figure 2: Study Schematic – Phase 2 Portion

AZA = azacitidine; CR = complete response.

- a Subjects may continue to receive repeated cycles of treatment until disease progression, relapse, unacceptable toxicity, or other discontinuation criteria are met.

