12.1.3 Reporting Periods for Adverse Events and Serious Adverse Events

The safety reporting period for all AEs and SAEs is from study Day 1 (predose) through 30 days after the last dose of study treatment (vadastuximab talirine or azacitidine). However, all study protocol-related AEs are to be collected from the time of informed consent.

All SAEs that occur after the end of safety reporting period (ie, more than 30 days after the last dose of study treatment) and are considered treatment-related in the opinion of the Investigator should also be reported to the Sponsor.

SAEs will be followed until significant changes return to baseline, the event stabilizes (recovering/resolving) or is no longer considered clinically significant by the Investigator, or the subject dies or withdraws consent, or study closure. All non-serious AEs will be followed through the safety reporting period.

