13.2 Sample Size Estimation

Phase 1 Portion (minimum of 6 subjects per cohort): Six subjects are adequate to appropriately assess the safety profiles and DLT rates of differing dose levels of vadastuximab talirine in combination with azacitidine. If the true incidence rate of DLT is 10%, the probability of considering a dose level tolerable (ie, ≤ 1 of 6 subjects experiences a DLT) will be 88.6%. If the true incidence rate of DLT is 50%, the probability of considering a dose level tolerable will be 10.9%.

Phase 2 Portion (106 subjects): A sample size of 106 subjects will provide 85% power to detect a treatment difference in ORR, assuming an ORR of 30% for azacitidine alone vs 55% for the combination of vadastuximab talirine with azacitidine, at a 2-sided 0.1 alpha level.

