13.6.7 Safety

Safety data will be summarized for the safety population separately for the Phase 1 and Phase 2 Portions by treatment arm or dose level.

Exposure to treatment will be summarized separately for vadastuximab and azacitidine. Summaries will include the duration of treatment, number of doses received, number of cycles received, number of doses interrupted and the reasons for dose interruption, the number of subjects with dose decreases for toxicity, the cumulative dose, and the relative dose intensity.

All AEs reported after initiation of treatment and pre-existing conditions that worsen after initiation of treatment will be considered treatment-emergent AEs (TEAEs). All AEs will be coded by system organ class, MedDRA preferred term, and severity grade using NCI CTCAE (v 4.03; [Appendix 18.4](#)). All recorded AEs will be included in the data listings.

The number and percent of subjects reporting all TEAEs, treatment-related AEs, SAEs, and deaths; TEAEs according to worst CTCAE grade; and AEs leading to treatment discontinuation will be summarized by preferred term and, where appropriate, system organ class. Deaths, SAEs, and AEs leading to treatment discontinuation will also be listed.

Adverse events that were considered DLTs will be listed and summarized by dose level for the DLT-evaluable population.

Summary statistics for actual values and for change from baseline will be tabulated as appropriate for laboratory results by scheduled visit. Where appropriate, laboratory results will be graded according to CTCAE 4.03, and shift tables from baseline to worst observed posttreatment grade will be presented.

All medications received during the treatment period will be considered as concomitant medications and will be coded by WHO medical dictionary and summarized.

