Clinical laboratory data (hematology, complete blood count [CBC] with differential, serum chemistry, inflammatory serologies, and specialty autoimmune serologies) will be presented graphically (mean and standard deviation) for selected laboratory tests, by treatment or dose level and scheduled visit. Summary statistics may be tabulated where appropriate. The worst post-baseline NCI CTCAE v4.03 will be presented by treatment or dose level and total for each laboratory test. Subjects with at least one on-study measurement for each laboratory parameter will be included, regardless of whether or not a baseline assessment is present.

Laboratory results and NCI CTCAE grades for hematology, and serum chemistry will be presented in data listings. Normal ranges will be documented and out-of-range values will be flagged by subject listings of grade 3 or higher abnormal lab results. Continuous summaries will be presented by clinical laboratory results, clinical visit, treatment group or dose level and study portion for actual results and changes from baseline. A shift table from baseline to worst observed post-baseline measure will also be presented.

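### Phase 2 adverse events are summarised only as crude percentages over an outcome-dependent window, so the between-arm comparison can mislead if treatment duration differs by arm

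*SAP*

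**What the plan says.** Protocol 13.6.7 plans summaries of this form: "The number and percent of subjects reporting all TEAEs, treatment-related AEs, SAEs, and deaths". SAP 9.6.1.2 does the same: "A summary table of number and percent of the following AE categories will be provided by treatment or dose level and total". Its list has some two dozen categories, including all TEAEs, SAEs, grade 3-5 events and drug-related events. Its counting rule is that "if a subject reports more than one AE that was coded to the same SOC or PT, the subject will be counted only once". For laboratory data, SAP 9.6.2 says: "The worst post-baseline NCI CTCAE v4.03 will be presented by treatment or dose level and total for each laboratory test". It sets no time limit on that worst value.

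Protocol 12.1.3 defines the collection window: "The safety reporting period for all AEs and SAEs is from study Day 1 (predose) through 30 days after the last dose of study treatment". Protocol Table 4 extends it to the end-of-treatment visit if that is later. Protocol 9.1.2 fixes no treatment length: "Subjects may continue on study treatment until disease progression, relapse, or unacceptable toxicity". Under Protocol 9.5.1.4.3 a subject is off treatment only when both drugs have stopped.

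SAP 9.3.1 tabulates duration of treatment, doses and cycles, but no adverse event table uses them as a denominator. Neither document plans an exposure-adjusted rate, a time-to-first-event or cumulative-incidence analysis, a common adverse event window, or a confidence interval for an adverse event difference.

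**The concern.** Evaluating the safety of the combination is a secondary objective, and the Phase 2 safety tables set the two arms side by side. What closes a subject's window is progression, relapse or toxicity, and these may differ by arm. The sample size itself rests on a difference in response, "assuming an ORR of 30% for azacitidine alone vs 55% for the combination".

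If the combination keeps subjects on treatment longer, they have more time to record a first event or a worse laboratory grade, even at the same underlying rate. If toxicity stops them sooner, a truly higher rate can look smaller or disappear. A reader who takes the percentages as a comparison at equal exposure could err in either direction and cannot correct for it by eye.

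**Working it through.** **The plan's own figure.** Protocol 13.2 states 85% power for 30% against 55% with 106 subjects (53 per arm) at two-sided alpha 0.10. The normal approximation gives 83.9% with pooled variance and 85.2% with unpooled variance, so the response rates are used below as stated. The documents give no adverse event rate and no treatment duration by arm. Everything that follows is therefore illustration under stated assumptions.

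**Illustration 1: duration driven by response.**

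Assume non-responders stay k0 = 3-6 cycles and responders k1 = 8-18 cycles, with the 30-day tail counted as about one cycle.

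- Mean window = ORR × (k1 + 1) + (1 − ORR) × (k0 + 1).
- Relative excess = (combination − control) / combination.
- Crude incidence at rate h per cycle = ORR × [1 − exp(−h(k1 + 1))] + (1 − ORR) × [1 − exp(−h(k0 + 1))].

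With h = 0.05 in both arms, so that the true rate ratio is 1:

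| k0, k1 | Control window | Combination window | Relative excess | Spurious difference |
|---|---|---|---|---|
| 3, 8 | 5.5 | 6.75 | 18.5% | 4.5 points |
| 6, 8 | 7.6 | 8.1 | 6.2% | 1.7 points |
| 4, 12 | 7.4 | 9.4 | 21.3% | 6.4 points |
| 3, 18 | 8.5 | 12.25 | 30.6% | 10.8 points |
| 6, 18 | 10.6 | 13.6 | 22.1% | 7.9 points |

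Worked line for 4 and 12 cycles:

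- 1 − exp(−0.25) = 0.221 and 1 − exp(−0.65) = 0.478.
- Control: 0.30 × 0.478 + 0.70 × 0.221 = 29.8%.
- Combination: 0.55 × 0.478 + 0.45 × 0.221 = 36.2%.

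Over the assumed range, the combination's mean window exceeds control's by 6%-31% of its own length. The model makes the combination window longer by construction, because it ignores stopping for toxicity.

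**Illustration 2: direction left open.**

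Assume exponential treatment duration with median m months, a 1-month tail and a constant first-event hazard h per month. Then crude incidence = 1 − exp(−h) × μ/(μ + h), with μ = ln 2/m. Fix the control median at 6 months and h = 0.10, which gives 51.5% in control.

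| Combination median (months) | Crude %, true ratio 1.0 | Difference | Crude %, true ratio 1.5 | Difference |
|---|---|---|---|---|
| 3 | 36.8 | −14.7 | 47.8 | −3.7 |
| 4 | 42.6 | −8.9 | 53.9 | +2.4 |
| 6 | 51.5 | 0 | 62.6 | +11.1 |
| 9 | 60.6 | +9.1 | 70.8 | +19.3 |
| 12 | 66.9 | +15.4 | not run | not run |

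For hazards of 0.05-0.20 and a true ratio of 1.0, the spurious difference is about 7 to 15 points in either direction at unequal medians, and zero at equal medians. Under this constant-hazard model, first events divided by person-time at risk return the true ratio in every row.

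**The case against.** A reader might infer that collection ends with treatment, that the arms will be observed for different times, and that the harm comparison is therefore biased. The documents do not support that.

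- **Collection outlasts treatment.** It continues for 30 days after the last dose of either drug and stays open while azacitidine alone continues. Treatment-related SAEs are reported later still (Protocol 12.1.3). SOS/VOD is reported to 180 days after the last dose of vadastuximab talirine or blinded drug (Protocol 12.1.4).
- **Unequal windows are a risk and not a documented fact.** No durations by arm are given, and longer response and earlier toxicity pull in opposite directions.
- **Some summaries already use common times.** SAP 9.6.2 plans laboratory values and changes from baseline by visit. SAP Section 5 and 9.6.1.3 give 30- and 60-day mortality from randomization with 90% confidence intervals. Exposure is tabulated, and the IDMC reviews unblinded safety data.
- **The tables are descriptive.** No between-arm adverse event test is planned. With 53 per arm, the 90% interval for 29.8% against 36.2% has a half-width of about 1.645 × √[(0.298 × 0.702 + 0.362 × 0.638)/53] = 15 points, more than twice the illustrated 6.4-point artefact.
- **A constant rate is doubtful.** Protocol 9.5.1.4.3 changes the dose after blast clearance for subjects who started above a stated level, so later person-time may differ from early person-time.

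All of these stand, and they limit the claim. They do not remove it. Mortality covers only death, and by-visit laboratory means do not repair the worst-grade table. The exposure tables are never linked to event counts. A crude percentage is a valid description of risk over the treatment-dependent window, but it is not a comparison at equal exposure.

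**Conclusion.** The point holds as a cheap improvement. Phase 2 adverse event categories and worst laboratory grade are summarised only as crude counts or percentages over an outcome-dependent window, with nothing planned to separate event rate from observation time. If durations differ by arm, those summaries can mislead as a between-arm comparison. The sign is unknown, and the distortion is zero if durations are equal.

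The sizes shown rest on assumed durations and constant hazards: 1.7 to 10.8 points in the response-driven illustration, and about 7 to 15 points in either direction when median durations are unequal. They show what is possible and do not predict this trial's result.

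**What to change.** Keep the crude percentages. In SAP 9.6.1.2, for Phase 2 TEAEs, grade 3-5 TEAEs and SAEs, add by arm:

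1. **Exposure-adjusted first-event rates.** Divide subjects with a first event by person-months from first dose to the earliest of first event, end of the adverse event reporting period, or death. Give a 90% confidence interval for the between-arm difference or ratio. State whether the period ends 30 days after last dose (Protocol 12.1.3) or at a later end-of-treatment visit (Protocol Table 4), and count events over that same period.
2. **Cumulative incidence over a common early window**, such as the first 6 cycles, which matches the unblinding milestone in SAP 9.5. Treat death as a competing event and show the number still under adverse event observation. Because collection closes soon after an early stop, add a sensitivity analysis that treats end of collection after stopping for progression or toxicity as a competing event.

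In SAP 9.6.2, show worst laboratory grade within the same early window. For SOS/VOD, use the protocol's own 180-day reporting period, so that events it deliberately collects are not cut off at 30 days.

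The cost is SAP wording and a few tables from dosing, onset and death dates already collected, with no new visits or subjects. Two limits remain. Exposure-adjusted rates assume a roughly constant hazard, and the early-window estimate is constrained where collection ends early. The two should be read together and stay descriptive.

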#### 9.6.1.3 Deaths and Serious Adverse Events

The number of total deaths (see definition in [Section 5](#)), deaths that occur within 30 days of last vadastuximab talirine treatment, and deaths that occur more than 30 days after last vadastuximab talirine treatment as well as the relationship to disease will be summarized by treatment or dose level and total. The number and percentage of subjects who died will be summarized by category of disease related or not. They will be also summarized in the same way and stratified by death date within or after 30 days of last vadastuximab talirine dose.

The 30-day and 60-day mortality rates (see definition in [Section 5](#)) and the associated 90% CIs will be summarized by treatment group.

Death information will be listed by subject. Additionally, listings of AEs leading to death and SAEs will be generated.

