9.5.1.4.3 Dose Modifications

Common toxicities including myelosuppression, nausea, gastrointestinal toxicity, fatigue, pyrexia, headache, weight decrease, dyspnea, rash, and stomatitis should be managed according to institutional standards or accepted guidelines (eg, American Society of Clinical Oncology [ASCO] guidelines for the use of WBC growth factors [26]). Growth factor support may be administered as needed according to institutional standard of care.

Vadastuximab Talirine

[Table 2](#) describes guidelines for dose modifications of vadastuximab talirine (Phase 1 Portion) or blinded study treatment (Phase 2 Portion) for toxicity.

Dose delays of any study treatment are permitted. If dosing is delayed for azacitidine, vadastuximab talirine (Phase 1 Portion), or blinded study treatment (Phase 2 Portion), both study treatments should be held and resumed together on the same schedule except when one agent is omitted during a cycle due to toxicity.

For patients who achieve a response to therapy, dose decreases, delays, or dose re-escalation (to original dose level) are permitted at the discretion of the medical monitor and site Investigator. Following achievement of marrow blast clearance to $<5\%$ (ie, a CR or marrow CR), patients originally treated with a dose higher than 5 mcg/kg of study drug will receive azacitidine with vadastuximab talirine (Phase 1 Portion) or blinded study treatment (Phase 2 Portion) as continuation therapy at the maintenance dose of 5 mcg/kg in subsequent cycles.

Azacitidine, vadastuximab talirine (Phase 1 Portion), or blinded study drug (Phase 2 Portion) may be permanently discontinued in the event of unacceptable related toxicity. Subjects will not be considered off study treatment until both study treatments are discontinued.

If subjects become candidates for stem cell transplant after enrollment, vadastuximab talirine must be discontinued at least 30 days prior to initiation of preparative regimen for stem cell transplant.

Table 2: Dose Modifications for Vadastuximab Talirine-Associated Toxicity

Category	Event	Action

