Hematologic toxicity with marrow blast count <5% ^a	≥ Grade 3 neutropenia or thrombocytopenia	Cycles of treatment may be delayed up to 14 days ^b until hematologic recovery is observed. Adequate hematologic recovery is defined as neutropenia and thrombocytopenia improved to < grade 3 (unsupported), OR ANC / platelets ≥ [(NADIR COUNT ^c) + (BASELINE COUNT ^d – NADIR COUNT) x 0.50] If hematologic recovery as defined above has not occurred within 14 days of the end of the cycle (by Day 42), omit vadastuximab talirine (Phase 1) or blinded study treatment (Phase 2) from the next cycle, and initiate next dose of azacitidine based on marrow cellularity as defined in Table 3.
Hematologic toxicity with marrow blasts ≥5% ^b	≥ Grade 3 neutropenia or thrombocytopenia	Treatment may continue without dose modification.
Clinically significant non-hematologic toxicity or asymptomatic non-hematologic laboratory abnormality (with the exception of hepatic toxicity)	≥ Grade 3 event	Treatment delay of up to 14 days is permitted until resolution of toxicity to < grade 3.
Laboratory evidence of hepatic toxicity (elevation in ALT, AST, or total bilirubin)	≥ Grade 3 event	Treatment delay of up to 14 days is required until resolution of toxicity to ≤ grade 1 or baseline. If toxicity has not resolved within 14 days, permanently discontinue vadastuximab talirine (Phase 1) or blinded study treatment (Phase 2)

ALT = alanine aminotransferase; ANC = absolute neutrophil count; AST = aspartate aminotransferase.

- a If cytopenias above grade 3 (e.g., ANC <1000/mm³ or platelets <50 x 10⁹/L) are present at Day 28 of a cycle in which no response assessment is required, an ‘unscheduled’ bone marrow biopsy is required within 14 days of the scheduled end of the cycle (eg, between Day 28 and Day 42). If the bone marrow cellularity is ≤10%, vadastuximab talirine or blinded study treatment will be permanently discontinued. If marrow cellularity is >10%, follow guidance as above.
- b Delays of >14 days may be permitted with approval of the medical monitor.
- c Nadir Count = the lowest count reached during the treatment cycle.
- d Baseline Count = counts prior to Cycle 1 of study treatment.

Azacitidine

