**Deaths:** Subject deaths will be determined from End of Study CRF page (where reason for discontinuation is death) and from AE CRF page (where CTCAE grade is 5 or outcome is “fatal”) and from the follow-up CRF page (where the answer to the question “Is the patient alive?” is “No”). The number of days between vadastuximab talirine or placebo last dose and death will be calculated as (date of death – last vadastuximab talirine or placebo dose date + 1).

**Dose-Limiting Toxicity:** see [Section 3.1.1](#).

**DLT Evaluable Subject:** is defined as all Phase 1 subjects who have completed at least Cycle 1 of treatment (Cycle 1 of treatment is completed when the patient receives the first dose of azacitidine on Day 1 of Cycle 2), or discontinued study treatment because of AEs or for a safety-related reason (defined as AE, Investigator Decision, or Progressive Disease) before having had

the opportunity to receive the first dose of azacitidine on Day 1 of Cycle 2, or who experienced a DLT.

**Duration of Response:** is defined as the time from first observation of response (PR+CR/Marrow CR) to disease progression/relapse or death from any cause, whichever occurs first.

**Duration of Treatment:** is defined as time from the first dose of any study drug until 28 days after the last day 1 dose date, or until : last contact date if the patient is still on treatment at the time of the analysis.

Minimum(Last day 1 dose date + 27, death date, last contact date) – first dose date +1

**Infusion Related Reactions AE:** is defined for those AEs that have responses of “Yes” for the question “Were there any infusion-related reactions?” in the CRF forms “Treatment – Blinded Study Drug”, “Treatment – Azacitidine”, or “Treatment – Vadastuximab Talirine”.

**Hematologic Improvement:** is defined in [Table 1](#)

**Hematologic Improvement (HI) Rate:** is defined in as the proportion of subjects with Erythroid response, Platelet response or Neutrophil response as defined in [Table 1](#).

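### The 30-day death split is timed from the last vadastuximab talirine or placebo dose and ignores azacitidine, so deaths on azacitidine alone can be tabulated as beyond 30 days

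*SAP*

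**What the plan says.** SAP 9.6.1.3 tabulates "deaths that occur within 30 days of last vadastuximab talirine treatment" against deaths occurring later. It uses the same cut for the summary by relationship to disease, which is "stratified by death date within or after 30 days of last vadastuximab talirine dose". SAP 5.0, under Deaths, gives the day count as "date of death – last vadastuximab talirine or placebo dose date + 1". The last azacitidine date enters none of these.

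The protocol treats the two drugs together when it decides whether a subject is on treatment. Section 9.5.1.4.3 states: "Subjects will not be considered off study treatment until both study treatments are discontinued". Section 12.1.3 says that the safety reporting period "is from study Day 1 (predose) through 30 days after the last dose of study treatment (vadastuximab talirine or azacitidine").

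The same protocol section lets the drugs part company. When counts have not recovered by Day 42, Table 2 says to "omit vadastuximab talirine (Phase 1) or blinded study treatment (Phase 2) from the next cycle, and initiate next dose of azacitidine". Table 2 also has vadastuximab talirine or blinded drug stopped for good, with no matching stop for azacitidine, for low marrow cellularity or for hepatic toxicity that does not resolve.

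**The concern.** A table of deaths within and after 30 days of last dose is usually read as separating deaths close to treatment from deaths in follow-up. Here a subject can be receiving azacitidine, be on study treatment by the protocol's rule and be inside its safety window, yet be counted in the later row because the other drug stopped earlier.

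Two smaller problems have the same source. The safety set admits anyone who received a single azacitidine dose (SAP 6.2), but vadastuximab talirine or placebo is first given on Day 7 or Day 9. A subject who dies before then has no date to count from. The added day in the SAP 5.0 formula also makes the 30-day class one day shorter than the protocol's window.

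At stake is how a descriptive mortality table is read, along with the relationship-to-disease summary built on it. The primary endpoint is not involved.

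**Working it through.** The plan states no figure for this point, so the check is date arithmetic.

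**Inputs**
- Cycles last 28 days. Vadastuximab talirine or placebo is given on the last azacitidine day, Day 7, or Day 9 on the alternate schedule (Protocol 9.1.1 and Table 4).
- SAP count = death date − last vadastuximab talirine or placebo date + 1 (SAP 5.0).
- Either-agent window ends at last dose of either drug + 30 (Protocol 12.1.3).
- Assumption: the SAP 5.0 count is the one compared with 30. SAP 9.6.1.3 gives no other count.

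**Cut-off.** A count of at most 30 means death no later than last dose + 29. After a Day 7 dose that is Day 36; after a Day 9 dose, Day 38.

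**Both drugs given on time.** The next vadastuximab talirine or placebo dose comes 28 days later, when the count is 28 + 1 = 29. Nothing is displaced.

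**One azacitidine-only cycle, on time (Day 29), after a Day 7 dose.** Azacitidine runs Days 29 to 35, with counts 23 to 29. The window ends on Day 35 + 30 = Day 65. Days 37 to 65, which is 29 days, are counted as beyond 30.

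**Omitted cycle after no recovery by Day 42, start on Day 43 assumed.** After a Day 7 dose, azacitidine runs Days 43 to 49, with counts 37 to 43, and the window ends on Day 79. All 79 − 43 + 1 = 37 days from the first azacitidine dose are beyond 30. After a Day 9 dose, azacitidine spans Days 43 to 51, with counts 35 to 43, and the window ends on Day 81. All 39 of 39 days are beyond 30.

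**Blinded drug stopped, azacitidine continued for k on-time cycles.** From the last vadastuximab talirine or placebo dose to the end of the either-agent window is 28k + 30 days. The SAP count keeps 29 of them within 30, so 28k + 1 fall beyond. Of these, 28k come from the choice of drug and 1 from the added day.

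| k | Days in window (28k + 30) | Counted as beyond 30 (28k + 1) |
|---|---|---|
| 1 | 58 | 29 |
| 2 | 86 | 57 |
| 4 | 142 | 113 |
| 6 | 198 | 169 |

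**Worked case.** Last blinded dose on Cycle 2 Day 7, azacitidine through Cycle 6 Day 7, death on Cycle 6 Day 20. From last azacitidine: 20 − 7 = 13 days. From last blinded dose: 4 × 28 + 13 = 125 days, or 126 by the SAP count. The death is also inside the SAP's own duration of treatment, which runs to the last Day 1 dose date + 27, here Cycle 6 Day 28.

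**Other outputs.** The 30- and 60-day mortality rates run from start of therapy (Phase 1) or randomization (Phase 2). Fatal treatment-emergent events (SAP 9.6.1.2) are not divided by time since last dose. No SAP table splits deaths by time since the last dose of any study treatment.

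**The case against.** The strongest reply is that the table does what its label says. The SAP never calls the two rows on-treatment and late, and SAP 5.0 defines study drug as vadastuximab talirine. Timing deaths from the investigational agent is therefore a coherent choice. Protocol 12.1.3 governs event collection, and Protocol 13.6.7 asks only that deaths be summarized and listed. A reader might infer that the SAP breaks a protocol rule for classifying deaths, but there is no such rule. This stands. It is a reason to keep the present split, though not to make it the only one when both drugs are study treatment.

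Nor are deaths lost. The event leading to death must be recorded, so the worked case would appear among fatal treatment-emergent events in its arm, as well as in total deaths and the listings. This also stands, and it limits the harm to one split.

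The affected group is narrower than it may look. When the last cycle contained both drugs, the two last-dose dates coincide. Where Table 3 delays azacitidine as well, deaths during that delay are classified alike under either anchor. Only subjects who actually receive azacitidine without the other drug can move.

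A reader might infer from SAP 9.6.1.3 that the comparator arm has no anchor, since only vadastuximab talirine is named. That section refers to SAP 5.0 for deaths, and SAP 5.0 counts from "last vadastuximab talirine or placebo dose date + 1". The comparator has an anchor, and only the wording needs aligning.

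The added day moves only deaths exactly 30 days after dosing. Inclusive counting appears elsewhere in the SAP, although its Appendix 4 uses last dose date + 30 without the extra day.

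**Conclusion.** The point holds in limited form. Deaths during azacitidine-only cycles, or within 30 days after them, are tabulated as beyond 30 days once more than 30 days have passed since the last vadastuximab talirine or placebo dose. Subjects who die before their first such dose fit neither row. For a subject with k on-time azacitidine-only cycles, 28k + 1 of 28k + 30 days are affected. With both drugs given on time, none are.

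These are days at risk, not deaths. The number of deaths affected cannot be computed, because the documents give no rates of azacitidine-only treatment or of death during it. A reader might infer that the experimental arm's on-treatment mortality is understated. The documents do not support that as a finding. A difference between arms is possible, because blinded drug alone is stopped for marrow or hepatic toxicity, but no stopping rates by arm are given, and Phase 1 has no comparator.

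The result rests on 28-day cycles, the SAP 5.0 count being compared with 30, and, for the omitted-cycle case, a Day 43 start. It is a worthwhile correction to a safety table and does not threaten the trial's main conclusions.

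**What to change.** - In SAP 9.6.1.3, make the main split within or after 30 days of the last dose of any study treatment, taken as the later of the last azacitidine and the last vadastuximab talirine or placebo dose. Apply it in both arms and both phases, and to the relationship-to-disease summary. Early deaths then have an anchor.
- In SAP 5.0, compute days as death date minus last dose date, without the added day, so that the class matches the protocol's 30-day window.
- Keep the vadastuximab talirine or placebo split as a secondary display, with a separate row for subjects who received neither. Add placebo to the wording of 9.6.1.3 so that it agrees with 5.0.

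The cost is one extra derivation and a table row, from dates already collected.
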